#### *Respiratory Measures:*

Minute ventilation (l/min) will be determined using a heated pneumotachometer and spirometer. A gas line will be run from near the mouth to a gas analyzer to determine inspired and expired Oxygen and Carbon dioxide. This data will be collected by having the participant breath through a mouthpiece (similar to a snorkel) during the baseline period. They will wear a nose clip during this time.

Pulmonary function will be determined by performing three or four respiratory maneuvers. This involves taking a full breath all the way in (maximal inhalation) and breathing out as fast as they can for 6 seconds (maximal exhalation). This will be done in the seated position using the same mouthpiece as described above. This will allow us to determine their lung capacity.

#### *Questionnaires and accelerometry (16-20 weeks; 26-28 weeks; 34-36 weeks, 2 months postpartum):*

Participants will be given links to (or paper copies of) the following questionnaires: 1) Health History Questionnaire which asks about the medical history (completed at the first visit only; however, some questions will be updated at each subsequent visit); 2) Pregnancy Physical Activity Questionnaire; 3) The Pittsburgh Sleep Quality Index which gives us an idea about the quality of you sleep over the past month; 4) a questionnaire asking about attitudes to exercise during pregnancy; and 5) Edinburgh Depression Scale which gives us an index of depression levels during pregnancy. In order to complete a 3 day food intake record, participants will receive a special login that is linked to their study ID (your name will not be linked to the account) which can be accessed by their computer or smartphone. A hard copy can be provided and returned to us by mail upon request. Participants will also be sent home with (or mailed) a 7-day Sleep Log where they will be asked to record when they go to sleep and when they wake up over the course of a week and asked to return both forms. At each time point participants will also be given an accelerometer to measure their level of activity (24 hours per day) for 7 consecutive days. In the postpartum, women will also fill in three questionnaires related to baby: 1) Infant behavior questionnaire, 2) brief infant sleep questionnaire, and 3) infant ages & stages – 2 months.

### **3.4 Statistical Plan**

#### *Sample Size Determination*

Our primary hypothesis is that exercise training will reduce resting SNA (burst/min) in pregnant women. Data from other clinical populations with high resting SNA indicates a ~23% decrease in resting SNA with exercise training (4). Previous data collected in our lab demonstrate a resting burst frequency of  $40 \pm 11$  burst/min. Based on previous findings we expect exercise training to reduce resting SNA to  $\sim 31 \pm 11$  bursts/min (-23%). Using these data we estimate 22 pregnant women are required to observe a significant reduction in SNA following exercise training (80% power,  $\alpha = 0.05$ ; G\*Power v3.16 (10)). We expect an 80% success rate for obtaining an appropriate SNA signal and an 80% retention rate, requiring 43 women to be recruited into the

training arm of the study. To allow for additional variability and or decreased retention we will recruit 50 pregnant women to take part in exercise training and 50 pregnant women to take part as controls.

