### 2.2. Hypotheses

- 1) *We hypothesize that exercise training will blunt the increase in SNA which occurs with pregnancy.*
- 2) *We hypothesize that vascular reactivity to sympathetic stressors will be reduced in women who are taking part in a structured exercise program compared to those that have not.*

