## 3 PATIENTS AND METHODS

### 3.1 Study Design

#### *General Design*

BASELINE (16-20 weeks), POST-INTERVENTION (34-36 weeks), AND POSTPARTUM (2 months): At each time-point during pregnancy, participants will report to the laboratory on two occasions. Women will report to the laboratory once in the postpartum.

**Visit 1)** Participants will complete a peak exercise test on the treadmill or bike to volitional fatigue. Instrumentation will include breathing through a mouthpiece attached to a metabolic cart (measures how and what the participant is breathing), heart rate, blood pressure and transcranial doppler ultrasound (TCD) to measure blood flow in the brain (middle cerebral artery). Resting diameter and flow of the internal carotid artery (ICA) will be assessed at rest. Lung capacity will be assessed at rest using spirometry. Participants will then warm up for 5 minutes at 3.4mph and 0% grade. After the warm up, the incline will increase in 1% increments until volitional fatigue. The test will be followed by a 5 minute cool down. Participants will hold the hand-rails through-out the peak test (5; 7). Exercise on the bike will follow a similar protocol of 5 minutes of rest, 5 minutes of warm-up at 0.5kpa. Exercise intensity will increase by 0.5kpa until volitional fatigue, followed by a 5 minutes of cool down and 5 minutes of rest.

**Visit 2)** Participants will arrive after refraining from exercise, caffeine, alcohol or food for 12 h (overnight fast) and blood samples will be collected. Following centrifugation, aliquots will be frozen at -80°C until analysis. A finger poke will be used to measure glucose via glucometer and blood gases and metabolites (blood gas analyzer). Following the blood draw, anthropometrics will be recorded and a standardized breakfast will be provided. Participants will then undergo an assessment of reflex neurovascular control. Participants will rest in a dentist chair 30° above supine for the duration of testing to minimize discomfort of the pregnant women.

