After instrumentation (described below) and an initial period of 20 min of rest, participants will undergo baseline testing which consists of arterial stiffness (pulse-wave velocity and ultrasound) and carotid distensibility. Next, participants will undergo 3 separate conditions separated by 20 minutes of quiet rest: **1)** 3 min with their hand in an ice bath (cold pressor test); **2)** Flow mediated dilation (~15 minutes) and **3)** an end expiratory breath hold (~15s). Following the cold pressor test a heating pad will be used to warm the hand to baseline temperature.

**Postpartum Visit)** Participants will arrive after refraining from exercise, caffeine, alcohol or food for 12 h (overnight fast) and blood samples will be collected. Following the blood draw, anthropometrics will be recorded and a standardized breakfast will be provided. Participants will then undergo an assessment of blood vessel health. After instrumentation (described below, but without microneurography), participants will undergo testing which consists of arterial stiffness (pulse-wave velocity and ultrasound) and carotid distensibility. Following this, participants will undergo an assessment of flow mediated dilation (described above).

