#### *Statistical Methods*

To assess our primary outcome (the difference in basal SNA between groups) a 2 way mixed model (group x time) ANOVA will be used. To assess the influence of exercise on our secondary outcomes (i.e. vascular function and blood markers) a similar 2 way mixed model design will be used. Tukey's post hoc analysis will be used to compare means when main effects are found to be significant.

The strength of the association between changes in SNA, vascular measures and blood markers within and across groups will be determined using the Pearson product-moment correlation coefficient. Statistical analyses will be performed using SPSS Version 16.0 (SPSS, Chicago, IL). Statistical significance will be assumed at  $P < 0.05$ .

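### The stated 80% power with 22 women is not shown for the planned between-group test; at 50 per arm, power for that test depends on a pre-post correlation that the plan does not give

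*Combined protocol and SAP*

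**What the plan says.** Under Sample Size Determination (section 3.4) the plan takes a resting burst frequency of 40 ± 11 bursts/min, expects about 31 ± 11 after training (a 23% fall), and sets 80% power and alpha 0.05. It concludes: "Using these data we estimate 22 pregnant women are required to observe a significant reduction in SNA following exercise training". It then inflates that number for the training arm only: "We expect an 80% success rate for obtaining an appropriate SNA signal and an 80% retention rate, requiring 43 women". A last step goes beyond 43: "To allow for additional variability and or decreased retention we will recruit 50 pregnant women to take part in exercise training", with 50 controls alongside. The section names the software, but not the test, the sidedness, a pre-post correlation or an expected change in controls.

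Statistical Methods, in the same section, defines the analysis: "To assess our primary outcome (the difference in basal SNA between groups) a 2 way mixed model (group x time) ANOVA will be used". The significance level is P < 0.05, again with no sidedness.

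SNA has two time points. The General Design says of 16-20 and 34-36 weeks: "At each time-point during pregnancy, participants will report to the laboratory on two occasions", and microneurography belongs to the second of those visits. The postpartum visit leaves it out: "After instrumentation (described below, but without microneurography), participants will undergo testing which consists of arterial stiffness".

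**The concern.** The power statement describes a fall after training, while the primary test compares two randomised arms. With two recordings per woman, the interaction compares the arms on change. Its precision depends on how strongly a woman's two recordings correlate and on what happens in controls, and the plan gives a value for neither. A reader who takes the 80% at face value would credit it to a test for which it was not shown. The yield step adds to the uncertainty: the two rates as written do not lead from 22 to 43, so the number of evaluable women expected from 50 recruits is unclear.

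**Working it through.** **Inputs from the plan.** Means 40 and 31, so the difference is 9 (9.2 if 23% of 40 is used); SD 11 at each visit; alpha 0.05; power 80%; 50 recruited per arm; signal success 0.8; retention 0.8.

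**Assumptions.** Two-sided testing; 22 read as per arm, because it is inflated for one arm; no change in controls; complete pairs; r from 0.15 to 0.7, which is not in the documents. All powers are from the noncentral t distribution unless stated.

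**Can 22 be reproduced?**
- Two-sided two-sample t test, 9/11: 25 per arm (24 for 9.2). With 22 per arm, power is 75.5% (77.3%). The normal approximation gives 24 (23).
- One-sided two-sample t test: 20 per arm (19).
- Two-sided paired t test in the training arm: 22 only if r is about 0.15 to 0.19 (0.11 to 0.15 for 9.2).

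Several readings come close, but the text does not say which was used.

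**Can 43 be reproduced?** 22/(0.8 × 0.8) = 34.4, so 35. 22/(0.8 × 0.8 × 0.8) = 22/0.512 = 42.97, so 43. The figure fits signal success at each of two recordings, times retention. Then 50 × 0.512 = 25.6 evaluable per arm. If the signal rate applies once, 50 × 0.64 = 32.

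**Power of the group x time test.** With two time points and complete pairs, the interaction test is a two-sample t test on change:

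SD of change = 11 × √(2(1 − r)); noncentrality = 9 / (SD of change × √(2/n)); df = 2n − 2.

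Example, r = 0.3: SD of change = 11 × √1.4 = 13.02. For n = 22, noncentrality = 9/(13.02 × 0.3015) = 2.29 and power is 61%. For n = 25.6, it is 9/(13.02 × 0.2795) = 2.47 and power is 68%.

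| r | n per arm for 80% | Power, 22 | Power, 25.6 | Power, 32 |
|---|---|---|---|---|
| 0.15 | 41 | 53% | 60% | 70% |
| 0.3 | 34 | 61% | 68% | 78% |
| 0.5 | 25 | 76% | 82% | 90% |
| 0.7 | 16 | 93% | 96% | 99% |

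The r at which power reaches 80% is 0.55 with 22 per arm, 0.48 with 25.6 and 0.34 with 32.

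**Power with baseline adjustment.** Compare the 34-36 week value between arms, adjusted for the 16-20 week value (ANCOVA): residual SD = 11 × √(1 − r²), df = 2n − 3.

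| r | n per arm for 80% | Recruits at yield 0.512 | Power, 25.6 |
|---|---|---|---|
| 0.15 | 24 | 47 | 83% |
| 0.3 | 23 | 45 | 85% |
| 0.5 | 19 | 38 | 91% |
| 0.7 | 14 | 28 | 98% |

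At r = 0 the residual SD is 11 and power with 25.6 is about 82%.

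**The case against.** The strongest reply is that the trial recruits 50 per arm, so 22 is not the number to judge it by. That stands: the relevant thresholds are 0.48 and 0.34, not 0.55, and at r = 0.5 power is above 80% under either yield.

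Other conditions also help the plan:
- Section 2.2 expects that "exercise training will blunt the increase in SNA which occurs with pregnancy". If controls rise while the training arm still falls by 9, the contrast grows. With 25.6 evaluable, a rise of 1.4 bursts/min at r = 0.3, or 2.5 at r = 0.15, restores 80%. The documents give no figure for the rise.
- Sidedness is unstated. With one-sided testing, the threshold at 22 per arm falls from 0.55 to about 0.42.
- The analysis is called a mixed model. If it is fitted by likelihood to all available recordings (assuming 40 baseline and 32 follow-up recordings per arm, 25.6 of them paired), power is roughly 72%, 78%, 88% and 98% over the same r. The plan does not say whether women with one recording are kept.
- Statistical Methods never says that the interaction is the decisive term. It is the natural reading, but an inference. A simple comparison of the arms at 34-36 weeks does not depend on r and gives 75.5%, 82% and 90% with 22, 25.6 and 32 evaluable.

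These points limit the conclusion. They do not supply the missing link between the stated power and the stated test.

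A reader might also infer that 43 is a miscalculation. The documents do not support that: 22/0.8³ gives it exactly after rounding up, and only the third factor is unwritten.

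**Conclusion.** The point holds as a gap between the power statement and the primary test. The 80% with 22 women is not shown for a between-arm comparison: even the simple two-sided comparison at one visit falls short at 75.5% (77.3% for a difference of 9.2), and the interaction reaches 80% with 22 per arm only if r is about 0.55 or more. At the planned enrolment, power for the interaction runs from 60% to 96% (25.6 evaluable) or from 70% to 99% (32 evaluable) over r from 0.15 to 0.7. This rests on two-sided testing, a difference in change of 9, SD 11 at both visits, no change in controls and complete pairs.

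It would be tempting to conclude that the trial is underpowered. The documents do not establish that: r and the change in controls are unknown, and a control rise, one-sided testing or use of all recordings would each lower the thresholds. The plan should be corrected, but there is no case here for changing enrolment.

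**What to change.** Keep 50 per arm.

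1. In Statistical Methods, make the primary analysis the comparison of 34-36 week burst frequency between arms, adjusted for the 16-20 week value (ANCOVA), two-sided at 0.05. The baseline recording is already planned.
2. In Sample Size Determination, replace the 22-woman power statement with one for that test, for example: *For a difference of 9 bursts/min between arms at 34-36 weeks, SD 11 and two-sided alpha 0.05, 50 women recruited per arm, with 80% signal success at each of two recordings and 80% retention (0.8 × 0.8 × 0.8 = 0.512), leave about 26 evaluable per arm. Baseline-adjusted power is at least about 82% even with no pre-post correlation.* If the sponsor meant the signal rate to apply once, state 0.64 and 32 evaluable instead.

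If the group x time ANOVA is kept, say that the interaction is the primary test and give its power by r as tabulated above, with the assumed control change and the handling of women with one recording.

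The cost is rewording in two places, with no change in enrolment or data collection. The downside is that either the primary analysis sentence changes, or the stated power becomes conditional on r and may fall below 80%.

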### 3.2 Subject Selection and Withdrawal

One hundred pregnant women (>18yrs, with singleton pregnancies) will be recruited between 16-20 weeks gestation through physician and midwife referrals, newspaper advertisements and recruitment posters. Women diagnosed with multiple pregnancies will be excluded. Eligible women will be randomized to take part in an exercise intervention (n=50) or no intervention (n=50). The intervention will consist of aerobic exercise equivalent to 50-70% of heart rate reserve, 3-4 times per week until the end of the study (34-36 weeks). For initial baseline testing (16-20 weeks) and at the end of the intervention (34-36 weeks), participants will visit the laboratory twice. Following initial baseline testing, women will be randomly assigned to an exercise intervention or no intervention. Women will receive an opaque sequentially numbered envelop with their allocation. Allocation will be determined using a randomly generated allocation sequence by an individual not associated with the research study who will place and seal the allocation in the envelope.

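### The loss allowance counts only women with usable SNA recordings at both visits; the primary analysis should be specified to use every usable recording

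*Combined protocol and SAP*

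**What the plan says.** All references are to the combined protocol and SAP.

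- **3.4, Sample Size Determination:** "we estimate 22 pregnant women are required to observe a significant reduction in SNA following exercise training". On losses: "We expect an 80% success rate for obtaining an appropriate SNA signal and an 80% retention rate". This leads to "requiring 43 women to be recruited into the" training arm, and then "we will recruit 50 pregnant women to take part in exercise training and 50 pregnant women to take part as controls". The section does not say whether the signal rate applies per recording or per woman.
- **3.4, Statistical Methods:** for the primary outcome, "a 2 way mixed model (group x time) ANOVA will be used", with Tukey comparisons, in SPSS. No analysis set or missing-data rule is given.
- **3.2:** "Following initial baseline testing, women will be randomly assigned to an exercise intervention or no intervention". Neither this section nor the eligibility criteria in 3.2.1 and 3.2.2 require a usable baseline SNA signal.
- **3.1, General Design:** nerve recording takes place at 16-20 and 34-36 weeks only. The postpartum visit uses the instrumentation "described below, but without microneurography".

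**The concern.** Microneurography is expected to fail in a fifth of attempts, so many women will have one usable recording and not two. Because randomisation follows baseline testing regardless of signal quality, a woman whose baseline recording failed can be randomised, complete the study period and give a valid recording at 34-36 weeks. A classical repeated-measures ANOVA deletes her, because it needs both values. It also deletes a woman with a good baseline who withdraws or whose final recording fails.

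What is at stake is precision on the primary outcome, and whether randomised women with an observed outcome at the end of the intervention are included. This is separate from whether to adjust for baseline: it concerns which women contribute.

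**Working it through.** **Inputs from the plan:** 22 evaluable women, signal rate 0.8, retention 0.8, 50 per arm, SD 11 bursts/min, expected difference 40 − 31 = 9 bursts/min. The 22 is taken as given. **Assumptions:** the loss rates, stated for the training arm, apply to both arms; retention is independent of signal success; pre-post correlation r, which the plan does not give, is 0.3, 0.5 or 0.7.

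**1. Reproducing the 43.**
- One signal factor and retention: 22/(0.8 × 0.8) = 34.4, so 35. This is not the plan's figure.
- Two signal factors and retention: 22/(0.8 × 0.8 × 0.8) = 22/0.512 = 42.97, so 43. This matches.

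With exactly two nerve-recording visits, the third factor reads as a usable signal at both. Multiplying the two rates also treats failures at the two visits as independent.

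**2. Recordings expected per arm of 50, independent failure.**
- Usable baseline: 50 × 0.8 = 40.
- Usable at 34-36 weeks: 50 × 0.8 × 0.8 = 32.
- Both: 50 × 0.512 = 25.6.
- Final only: 32 − 25.6 = 6.4, which is 6.4/32 = 20% of valid final recordings.
- Baseline only: 40 − 25.6 = 14.4, of which 40 × 0.2 = 8 are withdrawals and 6.4 are failed final signals.

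**3. If signal success correlates across visits.** With correlation φ, the chance of both signals is 0.64 + 0.16φ. At φ = 0.5 it is 0.72, giving 50 × 0.8 × 0.72 = 28.8 pairs, 3.2 final-only (10% of 32) and 11.2 baseline-only. At φ = 0.75 the final-only share is 5%.

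**4. Precision of the group-by-time effect.** For complete pairs, the variance of the mean change per arm is 2 × 121 × (1 − r)/25.6. For all recordings, the information per arm is I = 25.6 Σ⁻¹ + diag(14.4/121, 6.4/121), where Σ has variances 121 and correlation r. The variance of the change is (I₁₁ + I₂₂ + 2I₁₂)/det I. The SE of the between-arm difference is the square root of twice the per-arm variance.

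Worked at r = 0.5:
- Complete pairs: 2 × 121 × 0.5/25.6 = 4.727; SE = √(2 × 4.727) = 3.07.
- All recordings: I₁₁ = 0.4011, I₂₂ = 0.3350, I₁₂ = −0.1410, det = 0.1145. Variance = (0.4011 + 0.3350 − 0.2821)/0.1145 = 3.966; SE = √(2 × 3.966) = 2.82.
- Variance cut: 1 − 3.966/4.727 = 16%.

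| Assumed r | SE, pairs | SE, all | Variance cut, φ = 0 | Variance cut, φ = 0.5 | Power for 9 bursts/min, pairs vs all (φ = 0) |
|---|---|---|---|---|---|
| 0.3 | 3.64 | 3.23 | 21% | 14% | 70% vs 80% |
| 0.5 | 3.07 | 2.82 | 16% | 10% | 83% vs 89% |
| 0.7 | 2.38 | 2.26 | 10% | 6% | 97% vs 98% |

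SEs are in bursts/min at φ = 0. Power is two-sided at 0.05, normal approximation. If both analyses share a common baseline mean across arms, the cuts at φ = 0 are 19%, 16% and 11%.

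**5. Where the gain comes from.** Adding only the 6.4 final-only women per arm to the pairs, in the model without a common baseline mean, cuts variance by 7%, 5% and 3% at r = 0.3, 0.5 and 0.7. The rest of the gain needs the baseline-only recordings as well.

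**The case against.** **The plan excludes no one.** A reader might infer that women with one recording will be discarded. The documents do not say that. A recruitment allowance based on complete pairs is a cautious way to size a study and does not define the analysis set. The words mixed model could also describe a likelihood analysis that keeps these women. This stands: the exclusion is a reading, though the likeliest one given the ANOVA label and the Tukey comparisons. If a likelihood model was intended, the loss allowance does not match it, because women with only a final recording would contribute yet are counted as lost.

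**Bias is not shown.** A reader might infer that complete pairs are biased whenever loss is related to SNA. That does not follow for a randomised contrast. If loss depends on baseline SNA alike in both arms and the effect is constant, selection shifts the mean change by the same amount in each arm and cancels in the difference. Bias arises mainly when loss differs by arm or is related to the size of the effect, and the documents give no evidence of either. Nor is the mixed model's assumption always weaker: for a failed baseline recording, it requires that failure not depend on the unseen baseline value, which complete pairs can tolerate under the conditions just given.

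**The gain is modest, and the plan has budgeted for the loss.** It expects 25.6 pairs per arm against its own requirement of 22. The step 4 gains also depend on an assumed r and shrink as signal failures cluster within women. This stands and limits the weight of the point. It is not a reason to leave usable recordings out.

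**Conclusion.** The point holds as a recommended improvement to the primary analysis. It is firm that the 43 counts only women with two usable recordings and that the plan has no rule for women with one. It is an inference, though the natural one, that the ANOVA would omit them.

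On that inference, the loss per arm of 50 is about 6.4 of 32 final recordings and 14.4 of 40 baseline recordings under independent failure, or 3.2 and 11.2 if signal success correlates 0.5. The gain from using everything is a variance reduction of about 10% to 21% in the first case and 6% to 14% in the second, over r from 0.7 to 0.3. The upper figures rest on independent failure, and only a small part of the gain comes from women whose baseline recording failed. At r = 0.3 with independent failure, complete pairs fall below the plan's 80% power for its 9 bursts/min difference and using all recordings about reaches it. At higher r both exceed 80%. The trial stays interpretable without the change.

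**What to change.** In Statistical Methods, specify the primary SNA analysis as a likelihood-based linear mixed model (SPSS MIXED) with group, time and their interaction and an unstructured covariance for the two times, fitted to every usable recording from every randomised woman. A common baseline mean across arms is preferable, because randomisation follows baseline testing. State the missing-at-random assumption openly. Keep the complete-pair ANOVA as a sensitivity analysis. Report by arm how many women lack each recording and whether the reason was signal failure or withdrawal. In Sample Size Determination, say that the signal rate is applied at each of the two visits.

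The cost is SAP wording and a different procedure in the software already named. It needs no extra visits, data or participants.
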